7.1.1 Evaluation of Target Lesions

7.1.1.1 Complete Response

CR is defined as disappearance of all target lesions. Any pathological lymph nodes (whether target or non-target) must have reduction in short axis to < 10 mm from baseline measurement.

7.1.1.2 Partial Response

PR is defined as at least a 30% decrease in the sum of diameters (longest for nonnodal lesions, short axis for nodal lesions) of target lesions taking as reference to the baseline sum of diameters.

7.1.1.3 Progressive Disease

PD is defined as at least a 20% increase in the sum of diameters (longest for nonnodal lesions, short axis for nodal lesions) of the target lesions taking as reference the smallest sum on study (this includes the baseline sum if that is the smallest on study). In addition to the relative increase of 20%, the sum must also demonstrate an absolute increase of at least 5 mm (Note: the appearance of 1 or more new lesions is also considered progression).

7.1.1.4 Stable Disease

SD is defined as neither sufficient shrinkage to qualify for PR nor sufficient increase to qualify for PD taking as reference the smallest sum of diameters while on study drug.

7.1.2 Evaluation of Non-target Lesions

To achieve unequivocal progression on the basis of non-target lesions, there must be an overall level of substantial worsening in non-target disease such that, even in presence of SD or PR of target lesions, the overall tumor burden has increased sufficiently to merit discontinuation of therapy. A modest increase in the size of 1 or more non-target lesions is usually not sufficient to qualify for unequivocal progression.

7.1.2.1 Complete Response

For CR of non-target lesions, participants must have disappearance of all non-target lesions and all lymph nodes must be nonpathological in size (< 10 mm short axis).

7.1.2.2 Non-CR/Non-PD

Non-CR/Non-PD of non-target lesions is defined as persistence of 1 or more non-target lesions.

7.1.2.3 Progressive Disease

PD of non-target lesions is defined as unequivocal progression of existing non-target lesions or the appearance of 1 or more new lesions.

7.1.3 New Lesions

New lesion is defined as the new finding in an anatomical location on the follow-up scan assessment, exclude the impact of differences of scan technique. Such lesion that was not scanned at baseline is also considered a new lesion. The appearance of 1 or more new lesions is also considered progression.

7.1.4 Time Point for Response Evaluation

The overall response status at each time point for participants with measurable disease at baseline will be reported according to the [Table 1 Schedule of Assessments].

7.2 Safety Assessments

7.2.1 Laboratory Assessments

- See [Section 10.6 Appendix 6: Laboratory Assessments] for the list of clinical laboratory tests (including hematology, biochemistry, urinalysis and HbA1c) to be performed and refer to [Table 1 Schedule of Assessments] for timing and frequency.
- The investigator must review the laboratory report, document this review, and record any clinically significant changes occurring during the study as an AE. The laboratory reports must be filed with the source documents.
- Clinical significance of out-of-range laboratory findings is to be determined and documented by the investigator or subinvestigator who is a qualified physician. Abnormal laboratory findings associated with the underlying disease are not considered clinically significant unless judged by the investigator to be more severe than expected for the participant's condition.

Laboratory tests will be sent to the local laboratory for analysis and entered into eCRF. Clinical laboratory tests will be performed locally prior to dosing. Tests will be obtained as indicated in the [Table 1 Schedule of Assessments]. If hematology and biochemistry tests were performed within 7 days prior to the first day of dosing, they do not need to be repeated on Cycle 1 Day 1. Clinical laboratory tests at screening, at screening and on Cycle 1 Day 8 are to be performed after the participant has been fasting in order to ensure accurate interpretation of lab test values such as glucose values. Participant can take food after fasting blood samples are obtained. Fasting status will be recorded in source documents. Fasting is not necessary for laboratory tests performed at all other visits. HbA1c will be obtained at screening/baseline and EOT visits. If HbA1c is elevated ($\geq 6.5\%$), refer participant to appropriate provider during cycle 1 for glucose management. Lipid panel, including total cholesterol, high-density lipoprotein cholesterol (HDL-C), low-density lipoprotein cholesterol (LDL-C) and triglyceride tests, will be only obtained at screening.

Additional assessments may be done to monitor AEs or as required by dose modification requirements. Additional laboratory tests should be performed according to institutional standard of care.

For women of childbearing potential only, a serum pregnancy test will be performed at baseline. A urine or serum pregnancy test will then be repeated on Day 1 of each cycle prior to study drug administration at the EOT and follow-up visits till 6 months after the last dose of study treatment administration. Adequate contraception should be used by study participants during or after the last dose of study treatment administration per the requirement stated in [Section 10.2 Appendix 2 Contraception Requirements].

7.2.2 Vital Signs

Vital signs, including systolic and diastolic blood pressure (mmHg), pulse rate (beats/minute) and temperature will be obtained as indicated in the [Table 1 Schedule of Assessments]. All vital sign measures will be taken prior to dosing with the participant in the sitting or supine position.

If clinically significant vital sign changes from screening/baseline are noted, the changes will be documented as AEs on the AE page of the eCRF. Clinical significance will be defined as a variation in vital signs that has medical relevance as deemed by the investigator that could result in an alteration in medical care.

7.2.3 Physical Examination

Standard, full physical examinations will be performed to assess general appearance, skin, eyes, ears, nose, throat, neck, cardiovascular, chest and lungs, abdomen, musculoskeletal, neurologic status, mental status, and lymphatic systems. Physical examinations will be conducted at visits as outlined in the [Table 1 Schedule of Assessments]. Height measurement is only required at screening/baseline. Weight measurement will also be performed as indicated in the [Table 1 Schedule of Assessments]. If physical examination except for weight was performed within 7 days prior to the first day of dosing, it does not need to be repeated on Cycle 1 Day 1.

If clinically significant worsening of findings from baseline is noted at any study visit, the changes will be documented as AEs on the AE eCRF. Clinical significance is defined as any variation in physical findings, which has medical relevance that could result in an alteration in medical care. The investigator will continue to monitor the participant until the parameter returns to Grade ≤ 1 , or to the baseline condition, or until the investigator determines that follow-up is no longer medically necessary.

7.2.4 Electrocardiogram

Routine 12-lead ECGs will be performed and assessed using local standard procedures as indicated in the [Table 1 Schedule of Assessments]. If clinically significant worsening of a finding from baseline is noted, the abnormality will be documented as AEs on the AE eCRF. Prior to performing 12-lead ECGs, participants should rest in supine position (or semi-recumbent, if supine is not tolerated) for 10 minutes. ECGs will be read and assessed locally.

7.2.5 ECOG Performance Status

ECOG performance status [Section 10.7 Appendix 7: ECOG Performance Status Scale] will be evaluated at protocol-specified timepoints.

7.2.6 Ophthalmology Examination

Participants will have a complete eye examination at baseline performed by a qualified ophthalmologist or optometrist, including but not limited to: visual acuity (VA), best corrected visual acuity (BCVA), inter ocular pressure (IOP), extra ocular movement (EOM), pupils, external exam, slit lamp exam, and dilated fundoscopic exam. Eye exams performed during the study where clinically indicated will be at the ophthalmologist's discretion. Eye exams at EOT are required for participants who experience ocular AEs during the study and this at minimum must include VA, BCVA, and slit lamp exam.

7.2.7 Order of Assessments

Not applicable.

7.3 Adverse Events and Other Safety Aspects

The definitions of an AE or SAE can be found in [Sections 10.3.1 and 10.3.2], respectively.

AEs will be reported by the participant (or, when appropriate, by a caregiver, surrogate, or the participant's legally authorized representative).

The investigator and any qualified designees are responsible for detecting, documenting and recording events that meet the definition of an AE or SAE and remain responsible for following up AEs that are serious, considered related to the study drug, or that caused the participant to discontinue the study drug and/or study (see [Section 10.3 Appendix 3: Adverse Events: Definitions and Procedures for Recording, Evaluating, Follow-up and Reporting]).

The method of recording, evaluating, and assessing causality of AE and SAE and the procedures for completing and transmitting SAE reports are provided in [Section 10.3 Appendix 3: Adverse Events: Definitions and Procedures for Recording, Evaluating, Follow-up and Reporting].

7.3.1 Time Period and Frequency for Collecting Adverse Event and Serious Adverse Event Information

All SAEs will be collected from the signing of the ICF until 30 days following the last dose of study treatment or until initiation of a new anticancer treatment, whichever occurs first, at the time points specified in the schedule of assessments [Section 1.3] and reported on the eCRF.

All AEs will be collected from the signing of the ICF until the follow up visit at the time points specified in the schedule of assessments [Section 1.3] and reported on the eCRF.

If the NCI-CTCAE grade of an SAE/AE changes, the event should be relisted on the eCRF with the new NCI-CTCAE grade and new onset date.

If the NCI-CTCAE grade decreases, the SAE/AE should be relisted on the eCRF with the new NCI-CTCAE grade and new onset date. The exception is ongoing pre-dose events that continue post-dose and improve post-dose. Such events should not be re-listed.

If the NCI-CTCAE grade of an SAE reduces, the details of the AE should be provided on the SAE worksheet for the medical assessor to be able to assess the course of the event.

All SAEs will be recorded and reported to the sponsor or designee immediately and under no circumstance should this exceed 24 hours, as indicated in [Section 10.3 Appendix 3: Adverse Events: Definitions and Procedures for Recording, Evaluating, Follow-up and Reporting]. The investigator will submit any updated SAE data to the sponsor within 24 hours of it being available.

Investigators are not obligated to actively seek AE or SAE after conclusion of the study participation. However, if the investigator learns of any SAE, including a death, at any time after a participant has been discharged from the study, and he/she considers the event to be reasonably related to the study drug or study participation, the investigator must promptly notify the sponsor.

7.3.2 Method of Detecting Adverse Events and Serious Adverse Events

Care will be taken not to introduce bias when detecting AEs and/or SAEs. Open-ended and non-leading verbal questioning of the participant is the preferred method to inquire about AE occurrences.

7.3.3 Follow-up of Adverse Events and Serious Adverse Events

After the initial AE/SAE report, the investigator is required to proactively follow each participant at subsequent visits/contacts. All SAEs will be followed until resolution, stabilization, the event is otherwise explained, or the participant is lost to follow-up (as defined in [Section 8.3]). Further information on follow-up procedures is provided in [Section 10.3 Appendix 3: Adverse Events: Definitions and Procedures for Recording, Evaluating, Follow-up and Reporting].

If after the protocol-defined AE collection period (see [Section 7.3.1 Time Period for Collecting Adverse Event and Serious Adverse Event Information]), an AE progresses to an SAE, or the investigator learns of any (S)AE (serious adverse event or adverse event) including death, where he/she considers there is reasonable possibility it is related to the study drug or study participation, the investigator must promptly notify the sponsor.

7.3.4 Regulatory Reporting Requirements for Serious Adverse Events

- Prompt notification by the investigator to the sponsor of a SAE is essential so that legal obligations and ethical responsibilities towards the safety of participants and the safety of a study drug under clinical investigation are met.
- The sponsor has a legal responsibility to notify both the local regulatory authority and other regulatory agencies about the safety of a study drug under clinical investigation. The sponsor will comply with country-specific regulatory requirements relating to safety reporting to the regulatory authority, IRB/IEC and investigators.
- Investigator safety reports must be prepared for suspected unexpected serious adverse reactions (SUSAR) according to local regulatory requirements and sponsor policy and forwarded to investigators as necessary.

- An investigator who receives an investigator safety report describing a SUSAR or other specific safety information (e.g., summary or listing of SAEs) from the sponsor will review and then file it along with the Investigator's Brochure and will notify the IRB/IEC, if appropriate according to local requirements.

7.3.5 Disease-related Events and/or Disease-related Outcomes Not Qualifying as Adverse Events or Serious Adverse Events

Under this protocol, the following event(s) will not be considered as an (S)AE:

- Disease progression: events that are clearly consistent with the expected pattern of progression of the underlying disease are not to be recorded as (S)AEs. If there is any uncertainty as to whether an event is due to anticipated disease progression and/or if there is evidence suggesting a causal relationship between the study drug and the event, it should be reported as an (S)AE. All deaths up to 30 days after the final administration of study drug must be reported as an SAE, even if attributed to disease progression.

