9.4.3.1 Adverse Events

AEs will be coded using MedDRA.

An TEAE is defined as an AE observed after starting administration of the study drug and up to 30 days after the final administration of study drug. A study drug-related TEAE is defined as any TEAE with a causal relationship assessed as “yes” by the investigator.

The number and percentage of participants with TEAEs, drug-related TEAEs, serious TEAEs, drug-related serious TEAEs, TEAEs leading to withdrawal of treatment and drug-related TEAEs leading to withdrawal of treatment, TEAEs excluding SAEs will be summarized as deemed appropriate. The number and percentage of TEAEs by severity will also be summarized. The worst severity will be summarized if the same AE is recorded more than once for a participant.

AE data will be listed.

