10.3.1 Definition of Adverse Events

AE Definition:

An AE is any untoward medical occurrence in a patient or clinical study participant, temporally associated with the use of study drug, whether or not considered related to the study IP.

“Adverse event” means any untoward medical occurrence associated with the use of a drug in humans, whether or not considered drug related.

NOTE: An AE can therefore be any unfavorable and unintended sign (including an abnormal laboratory finding), symptom, or disease (new or exacerbated) temporally associated with the use of study IP. This includes events related to the comparator and events related to the (study) procedures.

Events Meeting the AE Definition

- Any abnormal laboratory test results (hematology, clinical chemistry, or urinalysis) or other safety assessments (e.g., ECG, radiological scans, vital signs measurements), including those that worsen from baseline, considered clinically significant in the medical and scientific judgment of the investigator (i.e., not related to progression of underlying disease).
- Exacerbation of a chronic or intermittent pre-existing condition including either an increase in frequency and/or intensity of the condition.
- New conditions detected or diagnosed after study IP administration even though it may have been present before the start of the study.

Events NOT Meeting the AE Definition

- Any clinically significant abnormal laboratory findings or other abnormal safety assessments which are associated with the underlying disease, unless judged by the investigator to be more severe than expected for the participant’s condition.

- The disease/disorder being studied or expected progression, signs, or symptoms of the disease/disorder being studied, unless more severe than expected for the participant's condition.
- Medical or surgical procedure (e.g., endoscopy, appendectomy): the condition that leads to the procedure is the AE.
- Situations in which an untoward medical occurrence did not occur (social and/or convenience admission to a hospital).
- Anticipated day-to-day fluctuations of pre-existing disease(s) or condition(s) present or detected at the start of the study that do not worsen.

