If an event is not an AE per definition in Section 10.3.1, then it cannot be an SAE even if serious conditions are met (e.g., hospitalization for signs/symptoms of the disease under study, death due to progression of disease).

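### Protocol 10.3.2 bars a progression death from being an SAE, while 7.3.5 requires every death to Day 30 after the last dose to be reported as one; 10.3.2 lacks the exception

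*Protocol*

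**What the plan says.** **Protocol 7.3.5** first says that events clearly in keeping with expected progression are not recorded as AEs or SAEs. It then makes an exception: "All deaths up to 30 days after the final administration of study drug must be reported as an SAE, even if attributed to disease progression".

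**Protocol 10.3.2** takes any event that is not an AE under 10.3.1 and says "it cannot be an SAE even if serious conditions are met". One of its two examples is "death due to progression of disease". It states no time limit and does not refer to 7.3.5.

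**Protocol 10.3.1** lists among things that are not AEs "The disease/disorder being studied or expected progression, signs, or symptoms of the disease/disorder being studied", unless more severe than expected for that participant.

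**Protocol 7.3** points to 10.3.1 and 10.3.2 for the definitions of AE and SAE. On reporting time for SAEs, 7.3.1 says "under no circumstance should this exceed 24 hours".

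**Collection window.** Under 7.3.1, SAEs are collected "until 30 days following the last dose of study treatment or until initiation of a new anticancer treatment", whichever is earlier; Table 1 footnote m says the same for AEs. After the window, 7.3.3 asks for events "including death, where he/she considers there is reasonable possibility it is related to the study drug or study participation". The TEAE definition in 9.4.3.1 runs "up to 30 days after the final administration of study drug", with no stop at new therapy, and SAP 4.5 uses the same 30 days.

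**SAP 4.5 and 4.5.1** take seriousness from the investigator's flag on recorded adverse events. A missing flag or a sponsor upgrade also counts. Fatal TEAEs are tabulated twice, once with and once without disease progression, and deaths are counted and listed separately.

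**The concern.** One event, an expected death from progression within 30 days of the last dose, must be an SAE under 7.3.5 and cannot be one under 10.3.2. The section that sites are told to consult for the definition names exactly this case and gives the opposite answer.

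Two things are at stake. The first is expedited reporting: a site following 10.3.2 owes no 24-hour report for such a death. The second is the safety table: a death never entered as an AE cannot appear as a fatal TEAE. The sponsor's upgrade in SAP 4.5 acts on recorded adverse events, so it does not clearly recover that death. Protocol 2.1 presents this as a bridging study meant to show safety consistent with the non-Chinese population, and a fatal-TEAE rate is a natural figure to compare.

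**Working it through.** The plan states no figure on this point, so there is none to reproduce. The check is a reading of the rules, followed by a scale for one death.

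**Step 1. One death, two rules.** Take a participant who dies of expected progression on or before Day 30 after the last dose, with no new anticancer therapy.

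| Rule | SAE? | 24-hour report? | Fatal TEAE recorded? |
|---|---|---|---|
| 7.3.5 | Yes | Yes | Yes |
| 10.3.2 with 10.3.1 | No | No | No |

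If the progression was more severe than expected, 10.3.1 allows it to be an AE and the two rules can agree. Without a switch of therapy, a death from any other cause in the window is an SAE under both. The conflict is therefore confined to expected progression deaths.

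**Step 2. Which rule is intended.** If progression deaths were never recorded as AEs, the two fatal-TEAE rows in SAP 4.5.1 would largely coincide. Planning both makes sense only under 7.3.5.

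**Step 3. Size of one death.** The denominator is the maximum enrolment of 40 (Protocol 9.2). Each affected death adds 1/40 = 2.5 points under 7.3.5 and 0 under 10.3.2. With 35 treated it would be 1/35 = 2.9 points.

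The number of such deaths, x, is not in the documents. For scale only, suppose 2 of 40 have fatal TEAEs not due to progression. The 2 is an assumption, near 40 × 7/125 = 2.24 from the EV-201 Cohort 1 count in Protocol 2.2.4. Clopper-Pearson 95% intervals:

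| x (assumed) | Fatal TEAEs, 7.3.5 followed | 95% CI | Row without progression |
|---|---|---|---|
| 0 | 2/40 = 5.0% | 0.6 to 16.9 | 2/40 |
| 1 | 3/40 = 7.5% | 1.6 to 20.4 | 2/40 |
| 2 | 4/40 = 10.0% | 2.8 to 23.7 | 2/40 |
| 4 | 6/40 = 15.0% | 5.7 to 29.8 | 2/40 |

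If every site followed 10.3.2, the first row would stay at 2/40 whatever x is.

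**Step 4. The collection window.** Suppose new therapy starts before Day 30 and the participant then dies, still before Day 30, of a cause judged unrelated. 7.3.5 wants the death reported and the TEAE window includes it. 7.3.1 has stopped collection, and 7.3.3 does not ask for it. This is a gap in collection, separate from the definition conflict. Table 1 places the end-of-treatment visit 30 days after the last dose and says that it should precede the next anticancer therapy, so the sequence should be uncommon.

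**The case against.** The strongest reply is that a specific rule governs a general one. Section 7.3.5 repeats the general exclusion of progression and then carves out deaths to Day 30 in mandatory terms, whereas 10.3.2 is an appendix definition with an illustrative example. This stands as evidence of intent. It does not remove the problem, because a site should not have to infer that an example naming its exact case does not apply.

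The safeguards also count. A quality tolerance limit watches for over- and under-reporting of AEs, monitors verify source data, and survival status is collected from the end-of-treatment visit onward. Deaths will therefore be known. None of these safeguards tells a site or monitor which rule is correct, since both are in the protocol.

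Safety is a secondary, descriptive objective. No threshold is set for fatal TEAEs, and nothing shows that sites will in fact split between the rules.

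A reader might infer that the serious and grade 3 or higher rows move by the same amount. The documents do not support that. Those rows count participants, so a death moves them only if the participant had no other qualifying event. In EV-201 Cohort 2, 67% had a grade 3 or higher TEAE and 30% an SAE, so the grade 3 or higher row in particular would often not move.

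A reader might also try to predict the number of affected deaths from EV-201. The protocol gives neither the share of early deaths attributed to progression nor whether the seven fatal TEAEs in Cohort 1 already include such deaths, so any prediction would be guesswork.

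**Conclusion.** The conflict is real and direct, and 10.3.2 is wrong as written. Section 7.3.5 is the intended rule. A site that applies 10.3.2 literally would omit both the 24-hour SAE report and the fatal-TEAE record for an expected progression death within 30 days of the last dose.

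The size is 2.5 points on the all-cause fatal-TEAE row per such death at n = 40. That rests only on the denominator; the number of such deaths is unknown, and the intervals above are illustrative. ORR, DOR, PFS, OS, PK, the plain count of deaths and the fatal-TEAE row without progression are not affected by the 7.3.5 and 10.3.2 conflict.

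The stop at new anticancer therapy is a secondary and narrow gap. It could lose an unrelated non-progression death from both fatal rows, but only when new therapy starts before Day 30.

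It would go too far to say that the plan leaves its intent open or that the study's conclusions are at risk. This is a wrong clause that should be corrected because the correction is nearly free.

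**What to change.** 1. In Protocol 10.3.2, add after the example: *except deaths up to 30 days after the last dose, which are reported as SAEs under 7.3.5*.
2. In Protocol 7.3.1, state that the 7.3.5 rule for deaths applies to Day 30 whether or not new anticancer therapy has started.
3. Before database lock, reconcile every survival-status death within 30 days of the last dose against the AE and SAE pages. This still works for deaths that occur before an amendment takes effect.

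The cost is two short protocol insertions and one check on at most 40 participants. The SAP tables and the TEAE definition stay as they are. The downside is that the headline fatal-TEAE row will include progression deaths, but the SAP already has the row that separates them out.
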